Zimbabwe	[name], University of Zimbabwe College of Health Sciences, Clinical Trials Research Centre, Harare [name], University of Zimbabwe College of Health Sciences, Clinical Trials Research Centre, Harare

Other Partner Organizations:

Medicines for Malaria Venture

[name], Director Clinical Operations
[name], Chief Scientific Officer
[name], Chief Medical Officer
[name], Director Access and Product
Management
[name], Director Business Development

University of Michigan
Center for Drug Repurposing

[name], PhD, Faculty Director
[name], Managing Director
[name], MD, PhD, Executive Sponsor

2 Summary

Objectives:
	
Primary Objective:
 
To determine the effectiveness of the trial intervention(s) in preventing symptomatic (i.e. any of the following: cough, shortness of breath or difficulty breathing, fever, chills, muscle pain, sore throat, new loss of taste or smell, nausea, vomiting, or diarrhea), laboratory test-confirmed COVID-19 in adults with repeated exposures to SARS-CoV-2 by day 60 after receiving trial interventions.
 
Secondary objectives:
 
 1. To determine the effectiveness of the trial interventions(s) in preventing symptomatic (i.e. any of the following: cough, shortness of breath or difficulty breathing, fever, chills, muscle pain, sore throat, new loss of taste or smell, nausea, vomiting, or diarrhea), laboratory test-confirmed COVID-19 in adults with repeated exposures to SARS-CoV-2 by day 150 after receiving trial interventions. 2. To determine the effectiveness of the trial interventions in mitigating the severity of COVID-19 in adults who become infected with SARS-CoV-2 by day 60 after receiving trial intervention. Severity will be graded on a simplified version of the ordinal WHO COVID-19 severity scale. 3. To determine the effectiveness of the trial interventions in mitigating the severity of COVID-19 in adults who become infected with SARS-CoV-2 by day 150 after receiving trial interventions. Severity will be graded on a simplified version of the ordinal WHO COVID-19 severity scale. 4. To determine the effectiveness of the trial interventions in preventing/reducing the incidence of SARS-CoV-2 infection (by serology) over up to 150 days (5 months) of follow-up (see trial duration per participant below).

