Main inclusion/exclusion criteria:	
Inclusion criteria
 
 1. Volunteers without clinical evidence of COVID-19 infection aged 18 years and older. 2. Participants who are at high risk of SARS-CoV-2 infection, defined as adults whose locations or circumstances put them at appreciable risk of exposure to SARS-CoV-2 and COVID-19. (see country specific addendum if needed to define further) 3. Must have a mobile phone and access to the Internet for data collection purposes. 4. Participants who are willing and able to provide informed consent via an electronic consent process. 
Exclusion criteria
 
 5. Weight outside range 50 kg – 120 kg (110 lbs – 265 lbs). 6. Self-reported or laboratory confirmed previous or current diagnosis of SARS-CoV-2. 7. Self-reported current acute respiratory infection. 8. Concurrent and/or recent use of the investigational product, a product considered to be equivalent to the investigational product, or any other product that is likely to interfere with the investigational products in this trial or the interpretation of trial data . 9. Self-reported known allergies to any of the IMPs and excipients of the IMPs and placebo. 10. Self-reported presence or history of the conditions listed in the appendices. 11. Self-reported current use of medication with known to interact with any of the medications listed in the appendices. 12. Inability or unwillingness to be followed up for the trial period.
Statistical methods and analysis:	The analysis of the primary endpoint will be by Bayesian logistic regression, adjusting for age as fixed effect, and sites as random effects. The secondary severity endpoint will be analyzed by Bayesian proportional odds model, with the same adjustment strategy. Interim analyses will be performed regularly for efficacy, futility and harm.

3 Background and Rationale

BACKGROUND

A. The Crisis of COVID-19

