Over the past few months, a health crisis wrought by the novel severe acute respiratory syndrome coronavirus-2 (SARS-CoV-2) has swept the world, taking a massive toll on people and nations; it has inflicted substantial societal and economic devastation, and threatens to overwhelm healthcare systems. This new deadly contagion has an estimated overall infection fatality rate of up to 2%.¹ It is a zoonotic infection that crossed to humans in late 2019, it rapidly causes mild to severe respiratory symptoms, and it is readily transmitted from human to human by droplet spread ($R_0 = 2.5$, compared to the 2009 H1N1 influenza pandemic that had an R_0 of 1.5; the R_0 of seasonal influenza is even lower). The resulting infectious disease has been termed COVID-19. Most infections are mild and similar in severity to the common cold. However, about 20-25% of those with documented infection have more severe symptoms, and approximately 5% of those infected have life-threatening complications (*Figure 1*),² including a severe acute respiratory syndrome, pneumonia, respiratory failure, sepsis, delirium, cardiogenic shock, acute kidney injury, liver injury, and multi-organ failure. SARS-CoV-2 belongs to the Beta-coronavirus family, which also includes severe acute respiratory syndrome coronavirus (SARS-CoV) and Middle East respiratory syndrome coronavirus (MERS-CoV).³ Some epidemiologists estimate that between 30% and 70% of the world's adult population could contract SARS-CoV-2 over the coming year, although this might be modifiable with appropriate behavioral modification and other measures.⁴ There is thus an urgent need to develop and deploy multiple behavioral and pharmacologic interventions in order to mitigate the harm of the current SARS-CoV-2 pandemic, as well as to inform management of future pandemics. In addition, the disease is likely to spread more easily between individuals living in vulnerable areas with condensed living conditions, including many low and middle-income countries, where large proportions of the population living together in close quarters. The extent of physical distancing that has proved effective in certain countries will not easily be implementable in many lower and middle-income countries, where living conditions are often informal, extremely dense and crowded. Furthermore, while suppression of the epidemic curve by physical distancing is known to be effective, it requires a high level of compliance that is unlikely to be maintainable for an extended duration even in economically advantaged countries, and it is economically and socially ruinous. Hence there is urgency to identify effective prophylactic, mitigation, and therapeutic options, as a bridge to the development of an effective vaccine. In response to this need, the COVID-19 Therapeutics Accelerator has been created as a collaborative initiative with contributions from an array of public and philanthropic donors, intended to support research and development in order to make effective COVID-19 treatments accessible to the world as quickly and as widely as possible. The **COVID-19 Research Outcomes Worldwide Network (CROWN) Collaborative** is a research platform, established with the intention of being one of the organizations to realize the vision of the COVID-19 Therapeutics Accelerator.

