2. To determine the effectiveness of the treatment arm(s) in mitigating the severity of COVID-19 in participants who become infected with SARS-CoV-2 by day 60 after commencement of trial intervention. Severity will be graded on a simplified Ordinal WHO COVID-19 severity scale.
3. To determine the effectiveness of the trial interventions in mitigating the severity of COVID-19 in adults who become infected with SARS-CoV-2 by day 150 after receiving trial interventions. Severity will be graded on a simplified version of the ordinal WHO COVID-19 severity scale.
- 4.
5. To determine the effectiveness of the trial interventions in preventing/reducing the incidence of SARS-CoV-2 infection (by serology) over up to 150 days (5 months) of follow-up (see trial duration per participant below).

5 Trial design

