11.1.2 Secondary outcomes

The following secondary outcome is of special interest: Severity of COVID-19 over the study period

- i) Uninfected – no clinical or virologic evidence of infection (Score = 0)
- ii) Ambulatory – no limitation of activities (score=1) or with limitation (Score=2)
- iii) Hospitalized – mild no oxygen (Score=3) or with oxygen (Score=4), hospitalized severe – Score=5-7*, dead (Score=8)

*Score 5 is non-invasive ventilation or high flow oxygen; Score 6 is intubation with mechanical ventilation; Score 7 is intubation with additional organ support (e.g. vasopressors, renal replacement therapy (RRT), extra corporeal membrane oxygenation [ECMO]).

These outcome definitions are based on WHO R&D Blueprint consensus definitions for COVID-19. The study period refers to the 60 days following commencement of trial intervention and an additional 3 months of observation period of participants i.e. 150 days in total. Moreover, severity will be reported based on a 60-day timeframe.

The secondary clinical outcomes consist of:

- Primary endpoint, but instead of the 60-day timeframe, over the course of the first 30 days after receiving trial interventions;
- Primary endpoint, but instead of the 60-day timeframe, over the course of the first 150 days after receiving trial interventions;
- Symptomatic COVID-19 (with subsequent virological confirmation) during the 150-day study period;
- Incident COVID-19 during the 60-day study period, which includes asymptomatic infections identified by serology samples taken at the time-point of study exit.

Table 4: Classification of Outcomes

Outcome	Baseline serology	60-day serology	150-day serology	RT PCR while symptomatic	COVID-19 symptoms
1. Nucleic acid confirmed COVID-19	+/-	+/-	+/-	+	+
2. Severe COVID-19	+/-	+/-	+/-	+	+ (scaled according to WHO ordinal severity scale)
3. Asymptomatic COVID-19	-	At least one of 2- or 5-month serology must be +	At least one of 2- or 5-month serology must be +	Not done	-
4. Presumed prior infection	+	+/-	+/-	- / not done	+/-
5. Other acute respiratory illness during trial	+/-	+/-	+/-	-	+

6. Symptomatic nucleic acid negative COVID-19; not primary outcome	-	At least one of 2- or 5-month serology must be +	At least one of 2- or 5-month serology must be +	-	+
--	---	--	--	---	---

Safety Outcomes

Safety outcomes will be determined according to the CTCAE (Common Terminology Criteria for Adverse Events) v5.0 27-Nov-2017 for grading severity of adult adverse events.

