11.2 Sample size and recruitment

11.2.1 Sample size calculation

We considered different event rates, depending on the following assumptions. Firstly, we assumed that 30-50% of the participants may become infected with SARS-CoV-2 over the course of the study period. Of these, the percentage of participants who will experience the primary endpoint or laboratory test-confirmed symptomatic COVID-19 (i.e. any of the following: cough, shortness of breath or difficulty breathing, fever, chills, muscle pain, sore throat, new loss of taste or smell, nausea, vomiting, or diarrhea) is uncertain. We use a range of 15-50%. The estimated event rate is therefore $0.15 * 0.30 = 0.045$ (or 4.5%, rounded to 5%) to $0.50 * 0.50 = 0.25$.

We declare the superiority of a treatment arm if the probability that the Odds Ratio (OR) of the treatment is less or equal to 1 is greater than 95%, i.e. $P(OR < 1) > 95\%$. The remaining Bayesian statistical triggers of the adaptive trial are specified in section 11.5.

A 2-arm trial was simulated to assess the required sample size for the study. The OR was assumed to be 0.7. Three event rates for control arm were used: 5%, 10% and 15%. We are interested in the lower end of the 5-25% range for the control rate since a higher sample size is required when the event rate in the control arm decreases for a given effect size.

Figure 5 below reports the probability that the simulated trial concludes superiority of the treatment arm depending on the sample size per arm.

[figure not shown]

Figure 5: Sample size estimation for the first phase of the trial (2-arm)

The simulations show that the probability of declaring efficacy depends on the event rate in the placebo arm. With 2000-2500 participants per arm, even if the event rate is 5% in the control arm, the study has >80% chance to declare efficacy.

We propose to retain the option of reaching a maximum of 2,500 participants per arm. We will aim to enrol a maximum of 5,000 participants in total in the first phase of the trial to allow for possible loss-to-follow-up (LTFU), withdrawal, protocol deviation, non-adherence and other methodological challenges. Further phases may be added to the trial until a maximum of 30,000 participants is reached.

The assumptions underlying the sample size calculations will be reviewed at each interim analysis based on the observed data.

11.2.2 *Planned recruitment rate*

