11.4 Statistical analysis plan

This section provides a general overview of the statistical analysis plan (SAP). A more detailed SAP will be written by the trial statistician and approved by the TMG and Data Monitoring Committee (DMC) prior to any substantial analysis of the data.

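### Severity objectives 2 and 3 concern participants who become infected, but the 0-8 proportional-odds OR, fitted in all randomised participants, mainly re-measures prevention

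*Combined protocol and SAP*

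**What the plan says.** The Summary (section 2) and section 4 both frame severity as a question about people who become infected. Section 4 has "To determine the effectiveness of the treatment arm(s) in mitigating the severity of COVID-19 in participants who become infected with SARS-CoV-2 by day 60"; the Summary has "To determine the effectiveness of the trial interventions in mitigating the severity of COVID-19 in adults who become infected with SARS-CoV-2 by day 60". Objective 3 asks the same at day 150.

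Section 11.1.2 makes severity the secondary outcome of special interest, on a scale from 0 to 8. The lowest category is "no clinical or virologic evidence of infection (Score = 0"; 1-2 is ambulatory, 3-7 hospitalised and 8 dead. In Table 4, row 2 (severe COVID-19) requires a positive PCR and symptoms, "scaled according to WHO ordinal severity scale".

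For the analysis, the Summary says "The secondary severity endpoint will be analyzed by Bayesian proportional odds model, with the same adjustment strategy", and section 11.4.2 repeats this. Only the covariate adjustment is carried over from the primary analysis.

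Section 11.6 opens by putting all randomised participants' data into an ITT analysis, then names ITT as the main strategy for the primary outcome. Its modified ITT set removes people already infected at baseline; it is not a set of people infected during follow-up. Section 11.4 leaves detail to a later document: "A more detailed SAP will be written by the trial statistician and approved by the TMG".

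**The concern.** The objectives condition on infection; the score and model do not. If the model is fitted to scores 0-8 in everyone randomised, most participants score 0, and the single OR is decided by how many leave that category. That is the prevention question, which the primary endpoint already answers.

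Section 3 (D) treats lower incidence and lower average severity as two different ways for an agent to be useful, so readers will want them kept apart. One common OR cannot do this. A purely preventive agent would appear to mitigate severity, and an agent that only keeps cases out of hospital would appear to do almost nothing. An agent that lowers incidence but worsens disease among cases could look favourable on the severity OR.

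**Working it through.** **Inputs.** Control event rates of 5%, 10% and 15% within a 5-25% range, OR 0.7, a maximum of 2,500 per arm, and a superiority rule of P(OR<1) > 95% (sections 11.2.1 and 11.4.2). On the event rate, section 11.2.1 says "We are interested in the lower end of the 5-25% range for the control rate". It also assumes that 30-50% become infected, so 30% and 50% scoring 1 or more are included as upper cases.

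Assumed here: a flat prior, no age or site terms, no dropout, and scores 1-8 among cases split .45, .33, .08, .08, .02, .015, .01, .015. This puts 22% at score 3 or more. The documents do not give a hospitalisation share. The nearest statement, in section 3 (A), is "about 20-25% of those with documented infection have more severe symptoms".

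**1. The plan's own figure (primary endpoint).** OR 0.7 from 5% gives odds 0.05/0.95 × 0.7 = 0.0368, so a rate of 3.55%. With 2,500 per arm and a one-sided 5% test, power is 81.2%, which agrees with the stated figure of more than 80%. (At 2,000 per arm it is 73.1%; that does not bear on this point.) No figure is stated for severity.

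**2. Information share, free of the severity mix and of any threshold.** Near the null, proportional-odds information is proportional to 1 - Σp_k³. Let p0 be the share scoring 0. The share of information carried by the 0 versus 1-or-more cut is then at least

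[1 - p0³ - (1-p0)³] / [1 - p0³],

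whatever the spread over scores 1-8. At p0 = 0.95 this is (1 - 0.857375 - 0.000125)/(1 - 0.857375) = 0.1425/0.142625 = 99.9%.

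| Share scoring 1 or more | 5% | 10% | 15% | 25% | 30% | 50% |
|---|---|---|---|---|---|---|
| Minimum share from 0 vs 1-or-more | 99.9% | 99.6% | 99.1% | 97.3% | 95.9% | 85.7% |

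**3. What the common OR returns (2,500 per arm, 20,000 simulated trials per setting).** The plan assigns no success rule to severity. P(OR<1) > 95% is borrowed for illustration only.

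| Scenario | Common OR at 5 / 10 / 15 / 25% | Declared a benefit |
|---|---|---|
| Prevention OR 0.7, severity among cases unchanged | 0.70 / 0.70 / 0.70 / 0.70 | 81 / 97 / 99 / 100% |
| Hospitalisation odds among cases halved, no prevention | 0.995 / 0.99 / 0.98 / 0.97 | 5 / 6 / 7 / 12% |
| All severity odds among cases halved, no prevention | 0.99 / 0.98 / 0.97 / 0.94 | 6 / 8 / 11 / 24-25% |

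At 30% and 50% scoring 1 or more, the third scenario gives ORs of about 0.92 and 0.85 and is detected in about 36% and 93%. A second assumed split (.40, .375, .10, .075, .02, .01, .01, .01) gives 37% and 94%. Under the final-analysis benefit trigger in section 11.5, P(OR<0.8) > 95%, the 5% column falls to 24% for the first scenario and 0% for the second. The stricter rule declares less but does not separate prevention from mitigation.

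**4. Opposite effects.** Take prevention OR 0.7 with hospitalisation odds among cases doubled, at a 5% rate.

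- Control: 2,500 × 0.05 × 0.22 = 27.5 expected hospitalised or dead.
- Treated: the odds 0.22/0.78 × 2 = 0.564 give a share of 36.1%, and 2,500 × 0.0355 × 0.361 = 32.0.
- The common OR is still about 0.70, declared a benefit in about 80%. The OR for score 3 or more is about 1.17.

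**5. Restricting the model to the infected.** At 5% this compares about 125 control cases with about 89 treated cases (2,500 × 0.0355). The groups are selected by an event after randomisation that treatment is meant to change, so randomisation no longer protects the comparison.

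**The case against.** - **The objectives and Table 4 row 2 can be read as an infected-only analysis**, under which the OR would not re-measure prevention. This is fair, and the documents do not exclude it. But the score then carries a category that the analysis never uses, and the comparison becomes the selected one in step 5. The first sentence of section 11.6 favours all randomised participants, so it would overstate the point to say that the plan gives no indication of the set.
- **The share scoring 0 is not fixed by the text.** A reader might infer that 75-95% score 0. That assumes only PCR-confirmed symptomatic cases score above 0. Table 4 row 6 (symptomatic, PCR-negative, seropositive) has clinical evidence of infection, and infections found only by serology are not placed. If more people score 1 or more, the OR detects more mitigation, as the 30% and 50% figures show, and the dominant cut becomes infection rather than the primary endpoint. The dominance itself survives.
- **The declaration rates borrow a rule.** A reader might take 81% as the chance that the trial will claim a severity benefit. The documents do not support that: no rule is assigned to severity, and no adaptation is tied to it.
- **The harm scenario is hypothetical.** Nothing in the documents suggests such an agent, and it should not be inferred that the harm would go unseen. Hospitalisation and death are SAEs, and the DMC reviews safety data. Those routes could flag it; the efficacy OR would not.
- **Scoring everyone is legitimate and the detailed SAP is still to come.** Both are true. An all-randomised ordinal analysis keeps randomisation and is not itself an error. The fault is using it to answer an infected-only objective, and the objectives, score and model are already set in the protocol.

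**Conclusion.** The mismatch is in the text and should be corrected. In all randomised participants the common OR is at least 97-99.9% a 0 versus 1-or-more comparison over the planned 5-25% range, and about 86-96% at 50-30%. This rests only on the scale, the model and the share scoring 1 or more. It does not answer objectives 2 and 3 as written.

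The simulated rates are illustrations that depend on the assumed severity mix, a flat prior and a borrowed threshold. The two forms of mitigation examined give different rates at higher event rates (about 12% against 24-25% at 25%). No separate event rate is given for day 150, so the 5-50% range serves both horizons. The primary analysis is unaffected.

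**What to change.** 1. Reword objectives 2 and 3 (sections 2 and 4) to the effect on the 0-8 score in all randomised participants, and name that analysis set in section 11.4.2 or the detailed SAP.
2. State that the common OR will not be reported as mitigation among the infected.
3. Beside the 0 versus 1-or-more OR, pre-specify an all-randomised contrast of score 3 or more (hospitalised or dead) against less than 3, using the Bayesian logistic model already planned for binary secondary outcomes. Label it as the effect on severe disease in all randomised participants.
4. Keep any infected-only summary descriptive, with its set and the selection caveat stated.
5. State how serology-only infections and Table 4 row 6 cases are scored.

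**Cost.** Wording, plus one model on data already collected. The contrast has few events. At a 5% rate with 22% of cases hospitalised or dead, the upper-to-lower ratio of its 90% interval is about exp(2 × 1.645 × √(1/27.5 + 1/19.5)) = 2.7 with 19.5 treated events and 2.9 with 15.4. For 0 versus 1-or-more it is about 1.6. Power for halved hospitalisation odds at 5/10/15% rates, under the borrowed P(OR<1) > 95% rule, is about 58/84/95%. At a 5% rate it falls to 39% or 26% if only 10% or 5% of cases are hospitalised or dead. The contrast also responds to prevention: with prevention OR 0.7 alone and 22% hospitalised or dead it declares benefit in about 31/48/59% at 5/10/15% rates. It must therefore be read beside the prevention OR and not as a pure measure of mitigation.

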5.1 Overall design

Study Design

CROWN CORONATION is a large, Bayesian adaptive, pragmatic, participant-level randomized, multi-site, international placebo-controlled trial. Randomization will be stratified by age (<50 and ≥50), site and previous vaccination with a SARS-CoV-2 specific vaccine. Participants will be individuals at risk of contracting SARS-CoV-2. Participants will be randomized to education and surveillance plus Placebo or to a study arm with active interventions for a period of up to 60 days. The details can be found in the relevant appendices.

All participants will require a mobile phone to participate. This is standard in all the countries in this study. The participant, with help from the local trial team if required, will enrol online using the web-based eCRF system and record basic demographic and eligibility information.

The database will be hosted on UK-based servers which are expected to be managed by Sealed Envelope Ltd. Local investigators will have access to the part of the CRF to enable recording of adverse events, outcome data and/or severity of COVID-19 symptoms. Participants will be sent emails with a link to complete an initial participant health questionnaire and the regular data logs.

Participants will complete weekly SMS surveys. Participants who develop symptomatic COVID-19 during the last month of observation will at a minimum be followed-up until symptom resolution and at a maximum until 150 days (5 months) after randomization (whichever comes first).

The study flow overview is outlined in *Figure 3*. In the case of oral medications, the trial will provide adherence support interventions that have been shown in randomized controlled trials to improve adherence to Human Immunodeficiency Virus (HIV) treatment and adapted for HIV Pre-Exposure Prophylaxis (HIV PrEP) (e.g. two-way SMS with check in for those that report symptoms or adverse events).

[figure not shown]

Figure 3a: Detailed chart outlining the likely flow for each participant in the trial. This may be modified by individual centers.

[figure not shown]

Figure 3b: Flow Diagram showing mixed use of internet and tele-messaging through the course of the trial.

Sites

CROWN CORONATION is an international, multi-site trial with sites in Canada, Ghana, India, Ireland, South Africa, UK, USA, Zambia and Zimbabwe. Sites will be selected in settings such as community-based clinics, general practice facilities and hospitals where IRB/REC approval is in place that the study can be conducted there. Access to laboratory testing and a research pharmacy are required. The research site will be associated with a healthcare facility or organization whose staff are considered to be at high risk of contracting COVID-19 and where there are personnel who have received adequate GCP and protocol training and are able to conduct the study procedures. Preferably, each site should be able to recruit at least 20 participants during the trial period although in rural locations, this number may be smaller. Consideration will also be given to whether there has been a report of COVID-19 outbreak in the local area, as this will increase the risk of individuals contracting the disease.

Participants

Participants will include adults (18 years or older) who are at risk for contracting SARS-CoV-2 based on their work in hospitals or in the community. See the country-specific addenda for country-specific definitions of individuals at risk for SARS CoV-2 exposure.

The reason that participants are at risk will be recorded in the CRF. Participants will be enrolled in low, middle, and high-income countries, including, Canada, Ghana, India, Ireland, South Africa, UK, USA, Zambia and Zimbabwe. Other countries may be added with time. All participants will be fully informed about the trial and will provide informed consent (electronically).

Baseline Data

At the time of enrolment, demographic information will be collected from participants, and relevant data on their medical histories, comorbidities, concurrent medication, and risk factors for severe COVID-19 will be documented. They will also provide information on the nature of their work and the contexts in which they are likely to encounter people infected with SARS-CoV-2. They will also provide information on their access to and use of personal protective equipment during high-risk encounters. In addition, they will be asked to nominate at least one other person to contact in case they become unwell so that we can establish what happened to them. This will all be done in line with local data protection legislation.

Interventions

As this is a pragmatic trial, other than administration of the intervention, all decisions regarding other measures taken to prevent SARS-CoV-2 infection or to mitigate its severity (e.g. use of personal protective equipment, limiting high risk exposures) will be at the discretion of the participant. Educational material regarding both social and clinical practice that could prevent or delay infection will be provided alongside trial information. The trial will track participants at a minimum of weekly for symptoms of infection and compliance with drug self-administration, and should participants contract SARS-CoV-2, we would offer them the option of participating in a treatment trial if it is available.

6 Investigational Medicinal Products (IMPs) and Non-Investigational Medicinal Products

